8.6.1 Dose Modification for Participants on inducers of CYP3A4 and/or PgP

Co-administration with strong inducers of CYP3A4 or P-glycoprotein (PgP) should be avoided when possible. Co-administration with moderate CYP3A4 or PgP inducers should be used with caution. That said, there may be participants on CNS agents known to be inducers of CYP3A4 (barbiturates, carbamazepine, oxcarbazepine, phenobarbital, phenytoin, valproic acid, benzodiazepines) that need to be continued on their medication regimen. No dosage adjustment of ABI-009 will be made for these participants; they will be dosed at the current stage of dose finding based on Table 3.

8.6.2 Dose Modification for Participants on inhibitors of CYP3A4 and/or PgP

Co-administration with strong inhibitors of CYP3A4 or P-glycoprotein (PgP) should also be avoided when possible. Co-administration with moderate CYP3A4 inhibitors (e.g., erythromycin, fluconazole) or PgP inhibitors should be used with caution. If the participant requires co-administration of moderate CYP3A4 inhibitors or PgP inhibitors, ABI-009 dose will be reduced to the next lower dose according to Table 3. (Additional dose reductions to every other day may be required to manage toxicities. If the inhibitor is discontinued the ABI-009 dose should be returned to the dose used prior to initiation of the moderate CYP3A4/PgP inhibitor after a washout period of 2 to 3 days. Seville orange, star fruit, grapefruit and their juices affect P450 and PgP activity. Concomitant use should be avoided.

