1.13 Comparison of Exposure of ABI-009 and Oral mTOR Inhibitors

Preclinical and clinical PK studies showed that ABI-009 administered IV exhibits an overall linear PK (C_{max} and AUC) with respect to dose. In contrast, oral rapamycin has poor bioavailability (14% with oral solution, 18% with tablet) and its uptake is affected by food [147]. The oral bioavailability is higher with everolimus at ~30% but is still heavily affected by food, which can reduce C_{max} by ~60% and AUC by ~16% [143]. Clinically, administration of ABI-009 at the maximum tolerated dose of 100 mg/m² IV weekly led to a much higher drug exposure as compared with daily oral rapamycin at 5 mg/day (C_{max} 130-200 fold, AUC 16-27 fold higher with ABI-009) and oral everolimus at 4-10 mg/day (C_{max} 50-70 fold, AUC 12-29 fold higher with ABI-009) [130, 143, 144]. The exposure normalized to dose (AUC/dose) is also significantly higher with ABI-009 compared with oral rapamycin (~3-5 fold) and oral everolimus (~4-5 fold) [130, 143, 144].

PK modeling and limited clinical data have also suggested that weekly IV administration of ABI-009 at doses similar to or lower than oral rapamycin and everolimus can achieve a weekly trough rapamycin blood level within the targeted therapeutic range of 5-15 ng/ml with oral mTOR inhibitors. In the current study, the starting dose of ABI-009 is 5 mg/m²/week, with potential dose escalation to 10 and 20 mg/m²/week or de-escalation to 2.5 and 1 mg/m²/week. Linear modeling of rapamycin blood concentration one week after ABI-009 IV administration using phase 1 clinical PK data indicates that a weekly dose of ABI-009 at 5-20 mg/m² can still maintain a relevant therapeutic weekly whole blood rapamycin trough level (see table below) with doses below 5 mg/m² reaching somewhat lower levels.

[figure not shown]
Table 1: Predicted Rapamycin Blood Levels after ABI-009 IV Administration

Dose (mg/m ²)	Time Post-infusion (hr)								
	0	1	4	8	24	48	72	96	168
1	28.44	9.45	7.40	5.20	3.64	2.43	1.42	1.39	0.71
2	56.88	18.89	14.80	10.39	7.27	4.86	2.84	2.79	1.42
3	85.32	28.34	22.20	15.59	10.91	7.29	4.26	4.18	2.13
5	142.20	47.23	37.00	25.99	18.18	12.15	7.10	6.97	3.56
10	284.40	94.46	73.99	51.97	36.35	24.30	14.20	13.94	7.11
20	568.80	188.92	147.98	103.94	72.70	48.60	28.40	27.88	14.22

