4 STUDY DESIGN

4.1 Study Overview

This is a prospective, single-center, non-randomized open-label phase 1 study to investigate multiple dose levels of ABI-009 for surgically-refractory epilepsy. Up to 18 participants are planned to be enrolled into the study.

The duration of participation for each participant is up to 18 weeks, including a 4-week baseline period to obtain baseline outcome rates, a 3-week active study period and a 12-week follow-up period (see Figure 1). After the baseline period, participants will be started on the assigned dose of ABI-009, given once weekly for a total of 3 weeks. Dose levels to be tested are below:

For dose finding, ABI-009 will be tested in cohorts of 3 participants each using the standard 3+3 dose-finding design. Initial starting dose will be at 5 mg/m²/week.

Table 3: ABI-009 Cohort Dosing Schedule

Dose levels	ABI-009 in mg/m ²
-2	1
-1	2.5
1	5
2	10

3	20
---	----

Escalation to the next dose level with a new cohort of 3 participants will occur after no DLT was observed. There will be no intra-participant dose escalation allowed. If a DLT occurs in a cohort, an additional 3 participants will be recruited to the cohort. If no further DLTs occur, then a new cohort of 3 participants at the next higher dose level can be enrolled. If 2/6 participants at a dose level experience a DLT, then the cohort will be closed to further enrollment and 3 participants will be enrolled at the next lower dose level, and so on. The MTD is the highest dose level in which ≤ 1 participant has a DLT. There will be no intra-participant dose escalation allowed.

Once the MTD has been determined, the MTD cohort will be opened for an estimated additional 6 participants. These participants will adhere to the identical protocol of the rest of their cohort.

Product will be administered IV every 7 days for 3 weeks.

For a detailed review of visits, please see Appendix 1.

Total duration of the study is expected to be about one year.

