8 STUDY DRUG DOSING

8.1 Method of Assigning Participants to Dosing Groups

Up to 18 eligible participants will be enrolled to receive the study drug (ABI-009). There will be no randomization, and this will be an open-label trial. Participants will be assigned according to a standard 3+3 dose escalation design, in the order that they are enrolled.

Participants must meet all inclusion criteria and no exclusion criteria should apply. The participant must have signed and dated an approved, current version of all applicable consent forms. To allow non-English speaking participants to participate in this study, bilingual health services will be provided in the appropriate language when feasible.

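### A dose level can be cleared in the 3+3 with fewer than three participants who received that nominal dose, because inhibitor users are dosed one level lower and no DLT-evaluable population is defined

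*Combined protocol and SAP*

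**What the plan says.** Section 4.1 sets the design: "For dose finding, ABI-009 will be tested in cohorts of 3 participants each using the standard 3+3 dose-finding design". The counting rule is by cohort. "Escalation to the next dose level with a new cohort of 3 participants will occur after no DLT was observed"; one DLT brings in three more participants, and "If 2/6 participants at a dose level experience a DLT, then the cohort will be closed to further enrollment". Section 8.1 fills the cohorts without regard to interacting drugs: "Participants will be assigned according to a standard 3+3 dose escalation design, in the order that they are enrolled".

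Two sections then separate the cohort from the dose or the exposure.

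- Section 8.6.2: for a participant who needs a moderate CYP3A4 inhibitor or a PgP inhibitor, "ABI-009 dose will be reduced to the next lower dose according to Table 3". Strong inhibitors are only to be avoided when possible.
- Section 8.6.1, for participants on AEDs that induce CYP3A4: "No dosage adjustment of ABI-009 will be made for these participants".

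Nothing says how a dose-reduced participant counts. The DLT definition (8.5) sets no minimum dose or number of doses at the level. Section 12.4 allows replacement only for participants who leave before any study drug or who fail the seizure minimum. Analysis by treatment received (15.1.1) is stated for the per-protocol analyses only. The DSMB meets before each escalation (section 14) but is given no evaluability criterion. Item 12 of section 10.4 allows dose changes at dosing visits only for toxicity, which conflicts with 8.6.2.

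**The concern.** DLT and MTD are primary endpoints (5.1), and the MTD fixes the dose for the six-participant expansion. A 3+3 decision rests on three to six people, so each one matters. If an inhibitor user in the 10 mg/m² cohort receives 5 mg/m² and has no DLT, the written rule offers no ground for leaving that person out of the three. The level would then be cleared on two people who received it.

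Inducer users raise a different issue. They do receive the cohort dose, but possibly at lower blood exposure, by an amount the documents do not give. DLT-free outcomes in a cohort with many inducer users may not carry over to participants who take none.

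**Working it through.** **The plan's own figures.** The plan gives no operating characteristics for its 3+3. The one related figure is the maximum of 18 participants. Three levels of 3 to 6 give 9 to 18 for escalation alone. Adding the 6 expansion participants gives 15 to 24. So 18 reproduces as the escalation maximum but not as the maximum including expansion. The points below do not depend on it, but the cost of the fix does.

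**Size of the dose step.** Section 1.13 gives the levels as a 5 mg/m² start "with potential dose escalation to 10 and 20 mg/m²/week or de-escalation to 2.5 and 1 mg/m²/week". From 20, 10 or 5 mg/m², one level down is a halving. Table 1 predicts 168-hour levels of 14.22, 7.11 and 3.56 ng/mL at 20, 10 and 5 mg/m², so the predicted trough also halves, before any interaction.

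**Information lost.** With no DLT among n participants, the one-sided 95% upper bound on the DLT rate is 1 − 0.05^(1/n): 63.2% for n = 3, 77.6% for n = 2 and 95.0% for n = 1.

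**Chance of clearing a level.** Let p be the DLT rate at the cohort dose, q = 1 − p, and r the DLT rate in the reduced participant. All rates are assumptions.

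- All three at the cohort dose: q³ + 3pq² × q³. For p = 1/3: 0.2963 + 0.4444 × 0.2963 = 0.428. For p = 0.40: 0.216 + 0.432 × 0.216 = 0.309.
- One of the first three reduced, any second three at the cohort dose: q²(1 − r) + [2pq(1 − r) + rq²] × q³.

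For p = 1/3 the bracket equals 4/9 whatever r is, so the second formula becomes 0.4444(1 − r) + 0.1317:

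| r in the reduced participant | Chance of clearing (p = 1/3) |
|---|---|
| 0.10 | 0.532 |
| 0.20 | 0.487 |
| 1/3 (reduction fully offset) | 0.428 |
| 0.50 (interaction outweighs reduction) | 0.354 |

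For p = 0.40 and r = 0.15: 0.306 + 0.462 × 0.216 = 0.406, against 0.309. With two of three reduced, p = 0.40 and r = 0.10: 0.486 + 0.432 × 0.216 = 0.579.

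**How often.** The documents do not give the share on inhibitors. If it is s, a cohort of three contains at least one such participant with probability 1 − (1 − s)³: 14.3% at s = 5% and 27.1% at s = 10%. Averaging over this with p = 1/3 and r = 0.10, the mean DLT rate in the first three is 0.05 × 0.10 + 0.95/3 = 0.3217, or 0.10 × 0.10 + 0.90/3 = 0.31. The chance of clearing is then 44.4% or 46.0%, against 42.8%.

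**The case against.** A reader might infer that the plan always errs towards clearing a level too easily. The documents do not support that. The reduction is tied to an interaction that raises exposure, and section 8.7.2 itself warns of higher mTOR inhibitor exposure with systemic imidazole antifungals. The size of the interaction is not given. A halved dose with an inhibitor may give lower, equal or higher exposure than the cohort dose, so the shift can be positive, nil or negative.

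A reader might also take the ten-point shift as typical. It is conditional on one of three being reduced for the whole course, and that may be uncommon. Inhibitors are to be avoided or used with caution (8.6.2), new chronic therapies are not to be introduced (section 7), and active infection is an exclusion (6.3). Section 8.6.2 speaks of returning to the dose used before the inhibitor was started, so a reduction may cover only some of the three doses.

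A third tempting reading is that inducer users shrink the denominator. They do not, because they receive the nominal dose. Estimating an MTD in participants on their existing AEDs is a defensible choice, and how many take inducers is not stated.

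Finally, no sentence says that dose-reduced participants count in full. That follows from an unqualified rule with no evaluability or replacement provision. The DSMB could notice such a case, since dose changes and concomitant medications are recorded, but it has no criterion to apply.

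All of this limits direction and size. It does not supply the missing counting rule.

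**Conclusion.** The point holds in a limited form. Followed as written, the plan can clear a level and name an MTD with fewer than three participants who received that nominal dose. This follows from 4.1, 8.6.2 and 12.4 together and needs no assumed rate.

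The effect on clearing does need one. If the reduced participant's DLT rate is below the cohort's, clearing is easier: 43% to 53% (rates of one third and 10%), or 31% to 41% (40% and 15%), when one of three is affected. Averaged over an assumed 5% to 10% inhibitor share, the first case shrinks to 1.6 to 3.2 points. With full offset it is nil, and only the dose label is wrong.

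For inducer users the conclusion is about carry-over: results may not extend to non-users, to an extent that cannot be calculated from the documents. The change is worth making because the primary endpoint is affected and the remedy is mostly wording.

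**What to change.** 1. Define a DLT-evaluable participant for escalation. A DLT-free participant who received less than the cohort dose for a non-toxicity reason does not count towards that level's 3 or 6 and is replaced. State how a reduction for only some of the three doses is treated. Extend 12.4 to match.
2. Count a DLT in such a participant against the cohort level. Moving it down to the dose received could make the cohort's level easier to clear.
3. Show the DSMB dose received, inducer or inhibitor status and trough beside each DLT outcome. Report DLTs and troughs by the same groupings.
4. Reconcile item 12 of 10.4 with 8.6.2, and the every-other-day reduction mentioned in 8.6.2 with weekly dosing. Which dosing rule applies is for the sponsor to settle.

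Cost: protocol and SAP wording. Concomitant medications (9.1.1), dose changes (8.6) and troughs (9.4) are already recorded. The counting rule leans towards caution. In a cohort with one inhibitor user, if a DLT in that person fills the place and otherwise one full-dose replacement does, the DLT rate for that place is r + (1 − r)/3 at p = 1/3. For r = 0.10 this is 0.40, and the chance of clearing is 0.4444 × 0.60 + 0.1317 = 0.398. With full offset it is 0.556, and the chance is 0.4444 × 0.444 + 0.1317 = 0.329. An occasional cohort needs an extra participant. Since the rules already allow 24 against a stated 18, the maximum must be checked before assuming that this fits.

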8.4.1 Dosage/Dosage Regimen

All participants receive study drug every 5-9 days for 3 weeks.

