8.6.3 Missed Study Drug Doses

Missed doses of study drug should be recorded. Our intention is to tightly adhere to the weekly schedule of medication administration.

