10.4 Visits 3, 4, & 5: ABI-009 Doses 1-3 (+/-2 days)

1. Review adverse events.
2. Review epilepsy diary.
3. Investigator opinion regarding seizures recorded: same, worse, somewhat better, better.
4. Record changes to concomitant medications.
5. Perform abbreviated physical exam
6. Measure and record height and weight.
 - a. BSA calculation (Calculated ONLY on Dose 1 visit; to be recalculated only if the weight changes by > 10% in subsequent cycles)
7. Obtain and record vital signs. Pulse oximetry must be >93 to continue.
8. Collect blood for clinical laboratory tests (chemistry, hematology).
9. Laboratory assessments as required per the schedule of evaluations
 - a. Complete Blood Count (CBC) with differential and platelet count
 - b. Blood chemistry assessment (required for Visit 4), including:
 - i. Sodium, potassium, chloride, bicarbonate, calcium, fasting glucose, albumin,
 - ii. Total protein, BUN, serum creatinine.
 - iii. Total bilirubin, AST, ALT, alkaline phosphatase, uric acid, phosphorus,
 - iv. Fasting serum lipid profile (total cholesterol, triglycerides, HDL and LDL)
10. Coagulation assessment, including prothrombin time, partial thromboplastin time, international normalized ratio (PT/PTT/INR)
11. Whole blood rapamycin trough levels
12. Dose modification as appropriate (only in the case of toxicities mandating a dose change as per section 8.6)
13. Administer study drug

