13 PROTOCOL VIOLATIONS

A protocol violation occurs when the participant, investigator, study staff or the Sponsor fails to adhere to the protocol requirements. Protocol violations for this study include, but are not limited to, the following:

- Failure to meet inclusion/exclusion criteria
- Inappropriate administration of study drug
- Failure of adherence to study schedule

Failure to comply with Good Clinical Practice (GCP) guidelines will also result in a protocol violation. The principle investigator will determine if a protocol violation should result in early permanent discontinuation of ABI-009 dosing for a participant.

When a protocol violation occurs, it will be discussed with the investigator and a Protocol Violation Form detailing the violation will be generated. This form will be signed by the Investigator. A copy of the form will be filed in the site's regulatory binder. The site will report the violation to their IRB in accordance with their IRB reporting requirements.

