APPENDIX 1. SCHEDULE OF EVENTS

	SCREENING DAY -14 TO DAY 0*	VISIT 1: DAY 0	VISIT 2: DAY 30**	VISIT 3: DOSE 1	VISITS 4&5: DOSES 2 AND 3	VISIT 6: ONE WEEK POST- DOSING	VISITS 7&8: 30 AND 60 DAYS POST-DOSING	VISIT 9: 90 DAYS POST- DOSING	EARLY PERMANENT DISCONTINUATION
Informed Consent Process	X								
Enrollment Eligibility Checklist	X								
Demographics	X								
Extended Physical Exam	X								
Neurological Exam	X								
Hepatitis C, and Hepatitis B, HIV if necessary ^A	X								
Epilepsy and Medical History	X								
Height, Weight, and BSA	X			X				X	X
Vitals	X		X	X	X	X			
Pulse Oximetry ^F	X		X	X	X				
CBC with Differential ^C	X		X	X	X	X	X ^B (visit 7 only)		X
Serum Chemistries with Coagulation Assessment ^E	X		X	X	X ^B (visit 4 required)	X ^B	X ^B (visit 7 only)		X
Urine Pregnancy ^G	X		X						
Study Continuation Checklist			X	X	X	X	X		
Abbreviated Physical Exam		X	X	X	X	X	X ^D		X
Concomitant Medication Review		X	X	X	X	X	X	X	X
Dispense Seizure Diary and Glossary		X							
Administer QOLCE, NCBRF, & C-SSRS			X			X		X	X
Review Seizure Diary			X	X	X	X	X		X
Investigator Opinion			X	X	X	X	X		
Dosing Checklist				X	X				
Study Drug Administration				X	X				
Adverse Events			X	X	X	X	X	X	X
Whole Blood Rapamycin Level ^H					X	X			X

*Screening may be combined with Visit 1

**Visit 2 may also be Visit 3 Dose 1

^A Hepatitis C (and if necessary, Hepatitis B) test: 2 mL SST gold top tube. HIV seropositivity test, if necessary: 2 mL gold top tube. If testing for all together, can use one 4 mL SST gold top tube.

^B Only if previous chemistries or coagulation profiles are abnormal or are otherwise clinically indicated.

^C CBC with differential: 1 mL EDTA lavender top tubes if testing with blood trough rapamycin levels. If testing alone can collect only 0.5 mL in EDTA tube.

^D Only at 30 days post-treatment

^E 2 x 4 mL SST gold top tubes. Serum chemistry: Na, K, Cl, CO₂, Ca, fasting glucose, BUN, creatinine, total protein, albumin, total bilirubin, aspartate aminotransferase (AST/SGOT), alanine aminotransferase (ALT/SGPT), alkaline phosphatase, uric acid, Ph, fasting serum lipid profile. Coagulation assessment: 1.8 mL Sodium Citrate light blue top tubes. Coagulation assessment including prothrombin time, partial thromboplastin time, international normalized ratio (PT/PTT/INR).

^F Must be greater than 93% on room air to continue with study procedures

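### Section 8.6.2 calls every-other-day dosing a reduction of a once-weekly infusion; it raises the frequency and could undo the required drop in weekly dose intensity

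*Combined protocol and SAP*

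**What the plan says.** The schedule is weekly wherever the protocol states it. Section 4.1: "Product will be administered IV every 7 days for 3 weeks". Section 8.4.1 sets the tolerance: "All participants receive study drug every 5-9 days for 3 weeks". Section 8.6.3 adds: "Our intention is to tightly adhere to the weekly schedule of medication administration". Section 10.4 and Appendix 1 provide three infusions, at Visits 3, 4 and 5, each with a window of 2 days either way.

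Section 8.6.2 covers participants who need a moderate CYP3A4 inhibitor or a PgP inhibitor. For them, "ABI-009 dose will be reduced to the next lower dose according to Table 3". The next sentence reads: "Additional dose reductions to every other day may be required to manage toxicities". It gives no amount per infusion and does not say whether the course stays at three doses.

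Section 10.4 refers staff to section 8.6 for dose changes made because of toxicity, so 8.6.2 is part of what they would consult.

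**The concern.** Every other day is a reduction only for a drug given more often than that, such as a daily one. For a drug given every 7 days it shortens the interval. The sentence presents the change as a way to lower exposure, and it points the other way.

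It applies to participants who already have toxicity and are taking a drug expected to raise rapamycin exposure. For them the one-level drop is the protection that 8.6.2 provides. Giving the reduced dose more often works against that drop. Staff would also hold two instructions, an interval of 5-9 days and an interval of 2 days, that cannot both be followed.

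**Working it through.** **Inputs.** Dose levels 1, 2.5, 5, 10 and 20 mg/m² (Table 3); three infusions (10.4, Appendix 1); interval 7 days, window 5-9 days (4.1, 8.4.1); one-level drop (8.6.2); predicted blood levels (Table 1, section 1.13); half-life about 60 h (section 1.10).

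**The plan's own figures.** Table 1 gives 14.22 ng/mL at 168 h for 20 mg/m², or 14.22 / 20 = 0.711 per mg/m². Scaling gives 10 × 0.711 = 7.11 and 5 × 0.711 = 3.555, printed as 7.11 and 3.56. The table is linear in dose and reproduces to rounding.

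**Interval.** Two days is below the 5-day minimum. As a rate it is 7 / 2 = 3.5 infusions per week against 1.

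**Seven-day dose.** Toxicity follows at least one infusion, and the next scheduled visit at which dosing can change is Visit 4, so at most two infusions remain. Assume that each is given at the full one-level-lower amount, 2 days apart. The ratio to the assigned weekly dose is 2 × lower dose / assigned dose.

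| Assigned (mg/m²) | One level down | Two infusions in 7 days | Ratio, every other day | Ratio, weekly at the lower dose |
|---|---|---|---|---|
| 20 | 10 | 20 | 20/20 = 1.0 | 0.5 |
| 10 | 5 | 10 | 10/10 = 1.0 | 0.5 |
| 5 | 2.5 | 5 | 5/5 = 1.0 | 0.5 |
| 2.5 | 1 | 2 | 2/2.5 = 0.8 | 0.4 |

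At every level this is twice the reduced weekly dose. Table 3 has no level below 1 mg/m², so that level has no corresponding row.

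**Course total over three doses.** If all three infusions are at the lower level: 30/60 = 15/30 = 7.5/15 = 0.5, and 3/7.5 = 0.4 from 2.5 mg/m². If dose 1 was at the assigned level: (20 + 10 + 10)/60 = 0.67, and (2.5 + 1 + 1)/7.5 = 0.60. The range is 0.4-0.67.

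**Exposure in the affected week.** The Table 1 single-dose profile was superposed, with log-linear interpolation and an exponential tail beyond 168 h (half-life 60 h or 72 h). For two lower-level infusions 2 days apart in week 2, the 7-day AUC relative to the unreduced weekly schedule is about 0.88 if dose 1 was also reduced and 0.95 if it was not. From 2.5 mg/m² the values are 0.70-0.71 and 0.78-0.79. A weekly schedule reduced throughout gives 0.50 (0.40). When all three doses are reduced, the peak in that week is about 0.54 (0.43) of the unreduced peak.

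**The case against.** The strongest reply is that the sentence will seldom, if ever, be acted on. It is permissive. Table 4 separately directs action for most toxicities: for example, a tolerable grade 2 non-hematological toxicity is continued at an unchanged dose, and higher grades generally lead to interruption or discontinuation. Table 4 gives no restart interval, but 8.4.1 sets 5-9 days for everyone. The trigger needs a qualifying inhibitor and a toxicity within a three-dose course. Strong inhibitors and systemic imidazole antifungals are to be avoided, and Appendix 1 has no visit for a 2-day infusion. If toxicity is recognised only around Visit 5, one infusion remains and no 2-day pair arises. All of this stands and limits the reach. It does not make the sentence correct, and no other text withdraws it.

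The amount is also unstated. Since the text speaks of a reduction, a reader could split the dose. The ratios above hold only if the full lower-level amount is repeated.

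Four stronger readings are tempting, and the documents do not support them:

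- *The one-level drop is cancelled altogether.* Only the 7-day dose returns to 0.8-1.0 times the assigned weekly dose. Course total and peak stay well below the unreduced schedule, and the AUC for that week stays somewhat below it.
- *Blood levels exceed those of the unreduced dose.* In Table 1, 10 mg/m² gives 24.30 ng/mL at 48 h, against 14.22 at 168 h after 20 mg/m². These are different times after infusion. At 48 h for both, the figures are 24.30 and 48.60, so the reduced dose still gives half.
- *The weekly dose rises above the assigned one.* A ratio of 3.5 × 10 / 20 = 1.75 needs infusions continuing every other day, which the schedule does not provide. A ratio of 3 × 10 / 20 = 1.5 needs all three doses every other day, so the change would have to be made within 2 days of dose 1, before any scheduled visit.
- *Following the sentence is a protocol violation.* Section 13 lists "Failure of adherence to study schedule", but 8.6.2 itself permits the change. The documents show two conflicting provisions, not a clear violation.

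**Conclusion.** The wording in 8.6.2 is wrong. A 2-day interval is an increase in frequency for this drug and contradicts 4.1, 8.4.1 and 8.6.3; that conclusion needs no assumption.

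Its size does rest on assumptions: the two remaining infusions are given 2 days apart, each at the full one-level-lower dose. The 7-day dose then equals the assigned weekly dose from 20, 10 and 5 mg/m², and is 0.8 of it from 2.5 mg/m². What is lost is the drop in weekly dose intensity during the toxicity, not the drop over the course. The AUC figures rest further on an adult single-dose linear model. Section 1.13 notes that pediatric PK data are lacking, and the inhibitor's effect on clearance is not modelled.

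This is a dosing-text error of limited practical reach that should be corrected. It does not affect the sample size or the planned analyses.

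**What to change.** Delete the every-other-day sentence in 8.6.2 and put in its place: *Toxicity at the inhibitor-reduced dose is managed according to Table 4 (pneumonitis: section 8.7.4), and the interval between infusions is kept at weekly or longer.* With a weekly interval the reduction holds: 0.5 of the assigned weekly dose, or 0.4 from 2.5 mg/m².

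The cost is one sentence in an amendment, with no change to visits, sample size or analysis.

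Two further edits are optional and separate. The first is a rule to hold or discontinue ABI-009 when Table 4 calls for a lower level and Table 3 has none. The second is to extend the dose-modification line in 10.4, now confined to toxicity, to the inhibitor-related reduction that 8.6.2 already requires.
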